#### **6.2.1.2      Overdose**

The effects of overdose of this product are not known. The daily AMG 330 dose may be up to 10% lower or higher in order to account for possible pump inaccuracies. A dose of up to 10% higher than the intended dose may not require specific intervention.

In case of overdose or medication error, the infusion should be immediately stopped. Consultation with the Amgen medical monitor is strongly recommended for prompt reporting of clinically apparent or laboratory adverse events possibly related to

overdosage. Consultation with the Amgen medical monitor is also strongly recommended even if there are no adverse events, in order to discuss the minimal duration of dose interruption. If the overdose results in clinically apparent or symptomatic adverse events, the subject should be followed carefully until all signs of toxicity are resolved and the adverse event(s) should be recorded / reported per Section 9. Resumption of AMG 330 is possible after consultation with the Amgen medical monitor and should adhere to the guidelines in Section 6.2.1.5.

A dose of >10% higher than the intended AMG 330 dose will be considered clinically important and classified as a serious adverse event under the criterion of “other medically important serious event” per Section 9.2.2.2.

#### **6.2.1.3 AMG 330 Outpatient Dosing**

If deemed stable by the investigator, a subject may continue AMG 330 cIV infusion as an outpatient. Subjects will receive a patient card indicating that the subject is participating in a clinical study. The patient card will also provide site contact details to be used in case of questions on the study or an emergency. In the outpatient setting, the subject will either return to the study site for infusion bag changes or the subject will be visited by a well-trained home health care service provider at specific intervals to change the infusion bag, measure vital signs, monitor and document adverse events and/or serious adverse events, and document any issues with the cIV infusion or infusion pump. The subject and home health care service provider will be trained and will receive written instructions for storage of the IV bags, if applicable. The home health care service provider will complete the study delegation log and will be authorized by the investigator before any study-related tasks are started.

Refer to the home health care manual for detailed information on the storage, handling, and administration of AMG 330, mandatory procedures, and data collection requirements.

Following each visit or telephone contact by the home health care service provider, the information collected will be documented on the Home Health Care Services visit worksheet and forwarded to the investigator. Any unexpected or unusual events as well as any deviations will be communicated promptly to the investigator. If any adverse event occurs in the outpatient setting, the home health care service provider should directly contact the site for further management. The home health care service professionals provide 24 hour emergency on-call service for any pump related issues. In the event of an interruption of the AMG 330 cIV infusion of > 4 hours, restart of the

infusion should be performed in the clinic/hospital under the supervision of the investigator or designee and the subject should be hospitalized for a minimum of 48 hours (see Section 6.2.1.5).

#### **6.2.1.4 Dose-cohort Study Escalation and Stopping Rules, Dose-limiting Toxicities (DLTs)**

For R/R AML (Group 1), dose escalation decisions will be made in accordance with a standard 3+3 design using the rules noted below.

- If no DLT is observed within the DLT window in the initial 3 subjects of a cohort, then dose escalation to the next higher dose level cohort will occur.
- If 1 DLT is observed within the DLT window in the initial 3 subjects of a cohort, then the cohort will be expanded to 6 subjects. If no further DLT(s) are observed in the 6 subjects, then dose escalation to the next higher dose level cohort will occur. If  $\geq 2$  subjects experience a DLT in a cohort, then enrollment into this cohort will be stopped.
- see Section 3.4 for replacement of subjects.

Dose escalation will occur at the planned dose levels until the MTD is determined or until the highest dose level is tested. The MTD is defined as the highest dose level with an observed incidence of DLT in < 33% of subjects enrolled in a cohort dose level. At least 6 evaluable subjects will be treated at the MTD or highest tested dose.

For MRD+ AML (Group 2) and MDS (Group 3), dose exploration will be guided by prespecified monitoring rules (Appendix H), which is based on a modified toxicity probability interval algorithm (mTPI-2; Guo et al, 2017) with a target DLT rate of 25% and an acceptable toxicity probability interval of 20%-30%. Consistent with conventional oncology phase 1 study designs (eg, 3 + 3 design) and given the imprecision with making decisions using as few as 3 subjects, in the instance of 1 DLT in the initial 3 subjects at a dose level then, as appropriate, the design allows expansion at the dose level beyond 3 subjects.

The mTPI-2 algorithm employs a simple beta-binomial Bayesian model. Let  $p_t$  be the target toxicity level and  $(p_t - \epsilon_1, p_t + \epsilon_2)$  be the equivalence toxicity interval denoted as EI. The unit toxicity interval  $(0, 1)$  is divided into subintervals with equal length given by  $(\epsilon_1 + \epsilon_2)$ . Let the under-dosing intervals (LI) denote for a set of intervals below EI, and the overdosing intervals (HI) for a set of intervals above EI. The 3 types of dosing intervals (EI, LI, HI) are associated with 3 different dose escalation decisions. The LI correspond to a dose escalation (E), the HI correspond to a dose de-escalation (D), and proper

dosing intervals (EI) correspond to staying at the current dose (S). This study design uses a target toxicity level,  $p_T$  of 25%, and EI of (20%, 30%).

Decision rules are based on the unit probability mass (UPM) calculated on these equal-length intervals. Given an interval and a probability distribution, the UPM of that interval is defined as the probability of the interval divided by the length of the interval. If the interval with the largest UPM is from LI, EI or HI, then the corresponding dose decision would be E, S, or D, respectively.

A dose level will be considered unsafe, with no additional subjects enrolled at that dose level, if it has an estimated 95% or more probability of exceeding the target DLT rate  $p_T$  (ie,  $P [DLT > p_T | \text{data}] > 95\%$ ) with at least 3 evaluable subjects treated and evaluated at that dose level.

After the escalation phase is completed, final DLT rates at each dose level will be estimated by isotonic regression (Ji et al, 2010). The MTD will be determined as the dose level with the DLT estimate closest to the target toxicity level of 25%. In the case of dose levels with estimated toxicity of equal distance (tied dose levels) from the target toxicity of 25%, the following approach will be used (Ji et al, 2010): among all tied dose levels the highest dose level with target toxicity  $\leq 25\%$  will be selected, unless all tied dose levels have estimated toxicity  $> 25\%$ , in which case the lowest dose level will be selected.

A DLT will be defined as any of the events described below occurring in a subject during the DLT window, unless clearly attributable to causes other than AMG 330. The DLT window will be 4 weeks, regardless of the length of the treatment cycle. The CTCAE will be used to assess toxicities/adverse events with the exception of cytokine release syndrome (see [Table 7](#) for grading of cytokine release syndrome).

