### **Dose Escalation**

For all MTDs (initial, subsequent and target doses), dose escalation will estimate the MTD. The estimated MTD is defined as the maximum dose at which fewer than

one-third of subjects experience a dose limiting toxicity (DLT) (minimum of 6 evaluable subjects for the target dose MTD; see Section 3.4 for definition of evaluable).

Dose Escalation will be conducted in two stages. In the single subject cohorts, single subjects will be enrolled at dose levels anticipated to be lower than those at which adverse events will be observed. Once higher dose levels are open for enrollment or when drug related safety or efficacy signals are observed (see below), the 3+3 design will be triggered.

Subjects who complete the DLT period (see Section 6.2.1.4) may proceed to a higher dose level for the following treatment cycle if no DLT has been reported for either this subject or any other subject in this dose cohort after completion of the DLT period, and once the next higher dose cohort is open for enrollment, after consultation with the sponsor (see Section 7.2.2 for details on assessments applicable in case of intra-subject dose escalation). DLTs experienced by subjects who proceeded to a higher dose as described above will not be considered for 3+3 decisions. However, the Dose Level Review Team (DLRT) may take this information into account to inform dose escalation recommendations.

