Should the initial dose be limited by adverse events related to first dose effects (eg, cytokine release syndrome), dose steps will be implemented. The MTD for the target dose will be estimated after giving the initial dose (and subsequent step doses if applicable) at their respective MTD(s). This means that the cohort for which a dose step will be implemented will start treatment for the first days at the first MTD assessed in the prior cohort. After this run in phase, there may be a dose increase to the next higher dose as per the dosing schedule shown in Table 4 of the protocol. If a 960 µg/day target dose is not the MTD, further dose escalation to a higher target dose up to 1.6 mg is allowed to reach MTD according to the rules described above. If this treatment schedule is tolerated, following dose cohorts will continue to receive the run in (initial) dose at the initial/1st MTD to assess the 2nd MTD. The target dose will be increased until a second MTD is reached. This 2nd MTD is the highest subsequent dose (day of dose step until end of cycle) with <33% of subjects experiencing a DLT. Each MTD will be estimated following 3+3 decision rules (Table 5). If additional dose steps are implemented, an MTD for each step will be determined using the same algorithm. To optimize the dose step schedule, additional intermediate steps below established MTD levels can be introduced based on DLRM recommendation.

The 1st run-in dose **and each** subsequent dose step should be administered for **1 to 5 days**. The treatment interval for all dose steps will be recommended by the DLRT based on the available safety, tolerability, PK, and PD data.

Starting with cohort 6, if there is an infusion free period of >24 hours between cycles, one or more dose steps in each cycle are mandatory for all subjects. Administration of a prophylactic steroid dose (8 mg IV dexamethasone) within 1 hour prior to the dose step for prevention of cytokine release is mandatory (see also Section 6.5). The additional assessments described in the schedule of assessments for dose steps ([Table 14](#)) apply. The DLRT may also recommend to implement additional dose steps in a cycle if this was considered appropriate and necessary to allow further dose escalation. The additional dose step(s) would be performed the same way as described above. In this case, an additional MTD would be estimated for the dose to be administered after the last dose step.

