**Table 5. 3+3 Dose Level Decision Rules**

# Subjects a	#Subjects with DLT	Decision
3	1	Enroll 3 additional subjects at same dose level
3	0	Escalate b
3	≥ 2	De-escalate c
6	1	Escalate b
6	≥ 2	De-escalate c

[figure not shown]
a Subjects who are not DLT-evaluable (see Section 3.4) are excluded from the count of subjects

b If final dose level has been reached, accrual will be suspended.

c If 6 subjects already entered at next lower dose level, the estimated MTD has been established.

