#### **10.3.1       Interim Analysis and Early Stopping Guidelines**

**Interim analyses are planned after all subjects in each indication and each phase have ended the study eg, for R/R AML: all subjects enrolled in Group 1 phase 1a, Groups 4 and 5 have ended the study. Interim analyses may be combined if the analysis timing is close or if the number of subjects in each indication or phase is small.**

Ad-hoc interim analyses for safety and preliminary efficacy updates will be performed. Data analysis prior to public disclosures (eg, scientific meetings) will also be performed. Safety data will be reviewed on an ongoing basis. Amgen, in consultation with the site investigators, will review in DLRMs all available cumulative data by indication prior to making dose escalation decisions. Adverse events and DLTs observed in all subjects will be evaluated continually by indication and fully integrated into all DLRMs and considered in all enrollment and dosing decisions.

Enrollment of a cohort can be suspended at any time based on safety findings at any dose level and in the expansion cohort, if at any time  $\geq 33\%$  of subjects treated at the MTD (including those treated at the MTD in the expansion phase) or RP2D experience a DLT within the DLT window, and a DLRM will be convened. In addition, the study may be discontinued or modified at any time due to documented safety findings.

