6.2 Dose Limiting Toxicity Evaluable Analysis Set

The DLT-evaluable Analysis Set includes all DLT-evaluable subjects. The analysis of DLT will be restricted to the DLT-evaluable Analysis Set. A subject is not DLT-evaluable if he/she drops out before completion of the DLT window for reasons other than an adverse event related to study drug or the subject has not received IP treatment for at least 14 days at the target dose for a 3- or 4-week cycle or at least 7 days at a target dose for a 2-week cycle. Furthermore, following drug interruptions, if a subject is unable to complete 2 repeat cycles for reasons other than DLT, the subject will not be DLT evaluable.

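### The Group 1 MTD sentence divides DLTs by subjects enrolled, which conflicts with Table 5 at 2 DLTs in 6 once a subject has been replaced; the 33% suspension rule has a similar, less consequential mismatch

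*Protocol*

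**What the plan says.** **MTD definition, Group 1.** Protocol 3.1.1 (multiple subject cohorts), Protocol 6.2.1.4 and SAP 7.1 share one sentence: the MTD is the highest dose level with "an observed incidence of DLT in < 33% of subjects enrolled in a cohort dose level". Protocol Section 5 treats a subject as enrolled once the first infusion starts, so the term covers every dosed subject. A second wording in 3.1.1 (dose escalation) asks for fewer than "one-third of subjects experience a dose limiting toxicity (DLT) (minimum of 6 evaluable subjects for the target dose MTD". It requires 6 evaluable subjects but does not say which subjects form the rate.

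**Decision table.** Footnote a of Table 5 reads: "Subjects who are not DLT-evaluable (see Section 3.4) are excluded from the count of subjects". Section 6.2.1.4 adds that if two or more "subjects experience a DLT in a cohort, then enrollment into this cohort will be stopped".

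**Analysis set.** SAP 6.2: "The analysis of DLT will be restricted to the DLT-evaluable Analysis Set". Protocol 10.1.2 says the same.

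**Replacement.** Protocol 3.4 replaces non-evaluable subjects during dose escalation. It gives no corresponding rule for the expansion.

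**Suspension rule.** Protocol 10.3.1 and SAP 7.1 allow enrollment to be suspended, and convene a dose level review meeting (DLRM), if the DLT rate reaches 33% or more; the rate is worded as "subjects treated at the MTD (including those treated at the MTD in the expansion phase) or RP2D experience a DLT within the DLT window".

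**The concern.** Three denominators are in use for one quantity: enrolled, treated and DLT-evaluable. Enrolled and treated counts include subjects who left early or had too little exposure at the target dose to be evaluable. While recruitment is open, the treated count also includes subjects still inside the 4-week DLT window. Provided these subjects add no DLTs to the numerator, they can only lower the rate, and so move it in the less cautious direction.

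Estimating the MTD is a primary objective of this first-in-human study. Its definition and its decision table should give the same answer on the same data.

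**Working it through.** **1. The plan's own figure.** The chance of at least one DLT is 1 − (1 − p)^n. For n = 3 it is 27.1% at p = 0.10 and 69.9% at p = 0.33. For n = 6 it is 46.9% and 91.0%. The stated 27–70% and 47–91% (Protocol 10.2) are reproduced.

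**2. No replaced subjects.** 1/6 = 16.7% is below 33%, and Table 5 escalates. 2/6 = 33.3% is not below 33%, and Table 5 de-escalates. The two rules agree.

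**3. With k replaced subjects, none of whom had a DLT.** The enrolled rate is d/(evaluable + k).

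| DLTs / evaluable | Table 5 | k | d / enrolled | Meets < 33%? |
|---|---|---|---|---|
| 2/6 | de-escalate | 1 | 2/7 = 28.6% | yes |
| 2/6 | de-escalate | 2 | 2/8 = 25.0% | yes |
| 3/6 | de-escalate | 3 | 3/9 = 33.3% | no |
| 3/6 | de-escalate | 4 | 3/10 = 30.0% | yes |
| 2/3 | de-escalate | 4 | 2/7 = 28.6% | yes, but fails the 6-evaluable minimum |

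**4. How often 2/6 could meet a replacement.** The documents give no non-evaluable fraction, so I assume 5%, 10%, 20% and 30%, independent of DLT. With q the evaluable fraction, the chance of at least one non-evaluable subject before six evaluable is 1 − q^6 = 26%, 47%, 74% and 88%. At a true DLT rate of 33%, the chance of one DLT in each set of three is (3 × 0.33 × 0.67²)² = 0.444² = 19.8%. The products are 5%, 9%, 15% and 17%. These are upper figures. They assume all three added subjects had entered before the second DLT was known, whereas enrollment stops at the second DLT.

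**5. Suspension rule, non-evaluable subjects.** For 3 DLTs in 10 treated with 8 evaluable: 3/10 = 30.0% (trigger not met) against 3/8 = 37.5% (met). For 9 DLTs in 30 treated with 27 evaluable: 9/30 = 30.0% against 9/27 = 33.3%.

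Now take a single look at 10 treated, with a true rate of 40% among evaluable subjects and no DLTs in the others (both assumed). As written, the trigger needs 4 DLTs, so its probability is P(Bin(10, 0.4q) ≥ 4). On the evaluable denominator, it is the binomial sum over the number evaluable.

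| Non-evaluable (assumed) | Evaluable denominator | Treated denominator |
|---|---|---|
| 10% | 69% | 51% |
| 30% | 67% | 30% |

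**6. Suspension rule, subjects still in the window.** Up to 30 expansion subjects in about 6 months (Protocol 3.3 and 3.5) is 5 per month, so about 5 could be in the 4-week window while recruitment is open.

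**7. A tempting repair for step 6.** One could count a subject as soon as a DLT occurs, but hold back DLT-free subjects until day 28. Start from 1/6 in escalation and add five expansion subjects, two with early DLTs and three DLT-free in the window. This gives 3/8 = 37.5%, against 3/11 = 27.3% of treated.

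I simulated this with 1/6 prior, ten subjects at about 5 per month, DLT onset within 10 days, a true rate of 20% and continuous monitoring. The trigger fires at some point in about 36–40% of trials, depending on fixed or random arrivals. As written it fires in about 13–15%, and with completed windows for both numerator and denominator in about 17%.

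**The case against.** A reader might infer that a dose rejected by Table 5 would be declared the MTD. The documents do not support that. Protocol 3.1.1 says "Each MTD will be estimated following 3+3 decision rules (Table 5", and Table 5 footnote c, on de-escalation, reads "If 6 subjects already entered at next lower dose level, the estimated MTD has been established". The final MTD and RP2D estimate uses all DLT-evaluable subjects (Protocol 3.1.5, SAP 3.1). Naming a 2/6 dose would need the MTD sentence to override all of these. They show which denominator was probably meant, but nothing in the text says which passage governs.

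A reader might also infer that a toxic expansion dose stays open. That does not follow either:

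- Protocol 10.3.1 allows suspension at any time on safety findings.
- Protocol 10.3.2 schedules dose level review team (DLRT) review after 5, 10 and every further 5 subjects, with ad hoc meetings.
- Safety data from non-evaluable subjects still reach the DLRM (Protocol 6.2.1.4).

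In-window dilution at exactly ten expansion subjects changes no enrollment decision. With 1/6 from escalation and 3 DLTs among 5 completers, 4/11 = 36% of evaluable contrasts with 4/16 = 25% of treated. But further enrollment waits until the first ten have completed a cycle plus two weeks or left the study. With the shortest cycle of 2 weeks, that is already the full 4-week window.

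What remains is a real textual conflict on the MTD, and a numeric trigger that can be missed through non-evaluable subjects or through in-window subjects away from that gate.

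**Conclusion.** The MTD sentence is wrong as written, because it contradicts Table 5, Protocol 10.1.2 and SAP 6.2. The conflict is narrow: essentially 2/6 with at least one replaced subject, or 3/6 with at least four. One replacement is enough to reverse the literal answer at 2/6 (33.3% against 28.6%). The frequencies in step 4 rest on an assumed non-evaluable fraction and are upper figures.

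The suspension rule's denominator is looser than the DLT analysis set and can miss the 33% trigger. That removes one numeric prompt for a DLRM. It does not by itself keep a dose open.

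The documents also leave unstated whether the final Group 1 estimate applies the 33% limit or the Table 5 rule to the pooled evaluable data.

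**What to change.** 1. **MTD sentence** (Protocol 3.1.1 and 6.2.1.4, SAP 7.1). Reconcile it with Table 5 by replacing *subjects enrolled* with *DLT-evaluable subjects* in a cohort dose level.
2. **Evaluability** (Protocol 3.4 and 6.2.1.4, SAP 6.2). State that a subject with a DLT counts as evaluable. Otherwise the minimum-exposure clause, read literally, could drop a subject whose DLT came early. Protocol 6.2.1.5 suggests this is not intended.
3. **Suspension rule** (Protocol 10.3.1, SAP 7.1). At scheduled DLRT reviews, compute the 33% on the DLT-evaluable set. If the rate is also monitored continuously, use only subjects whose window has closed, in both numerator and denominator. Do not count DLTs at once while holding back DLT-free subjects, because that inflates the rate (step 7). The existing provision to suspend on any safety finding covers DLTs that arise before windows close.

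The cost is wording in two documents. The downside is that the trigger, and so a DLRM, may be reached somewhat more often.

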### DLT Evaluation

A subject is not DLT-evaluable if he/she drops out before completion of the DLT window for reasons other than an adverse event related to study drug **or the subject has not received IP treatment for at least 14 days at the target dose for a 3- or 4-week cycle or at least 7 days at a target dose for a 2-week cycle**. All available safety data for subjects who are not DLT evaluable will still be evaluated and considered in DLRM decisions. No dose escalation will occur unless at least 3 subjects have **been assessed as DLT evaluable**. Duration of a cycle might be extended and be different from the duration of the DLT window. For all cohorts, the DLT window may also be extended

retrospectively to assess events starting or persisting outside the window in case the DLT definition is time dependent (eg, in case of neutropenia, see below).

Any adverse event occurring outside the DLT window that is determined by the investigator to be possibly related to the investigational product, which is seen more frequently or is more severe than expected or is persistent despite appropriate management, can be determined to be a DLT upon unanimous decision by the DLRT after review of the adverse event and all available safety data.

Events listed below are to be considered as DLTs and exceptions when occurring in a subject during the DLT window unless clearly attributable to causes other than AMG 330 treatment:

- Any treatment-related death.
- Grade 4 neutropenia lasting  $\geq$  42 days from start of cycle in absence of evidence of active AML (in case of 3 or 4 weeks treatment cycles, the number of days would increase accordingly)
- Grade 3–5 non-hematologic toxicity not clearly resulting from the underlying leukemia EXCEPT:
  - Alopecia
  - Grade 3 fatigue, asthenia, fever, anorexia, or constipation
  - Grade 3 nausea, vomiting or diarrhea not requiring tube feeding, total parenteral nutrition, or requiring or prolonging hospitalization
  - Infection, bleeding, or other expected direct complication of cytopenias due to active underlying leukemia
  - Grade 3 infusion reaction, if successfully managed and which resolves within 72 hours
  - Grade 3 rash
  - Grade 3 or 4 tumor lysis syndrome if it is successfully managed clinically and resolves within 7 days without end-organ damage.

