**Table 6. Assessments to be Performed After Infusion Interruption and Restart**

Length of Cycle	Length of Infusion Interruption	Dose level at which interruption occurred	Assessments to be performed
2 weeks	≤ 24 hours	Run-in dose, dose step or target dose	Continue following schedule of assessments per protocol
	> 24 hours	Run-in dose, dose step or target dose	Repeat the cycle and schedule of assessments ( Table 8 or Table 9 ) starting at day 1, perform dose step assessments as needed per Table 14
3 or 4 weeks	≤ 24 hours	Run-in dose, dose step or target dose	Continue following schedule of assessments per protocol
	> 24 hours < 7 days	Run-in dose or step dose	Repeat the cycle and schedule of assessments ( Table 9 – Table 23 ) starting at day 1, perform dose step assessments as needed per Table 14
	> 24 hours but < 7 days	Target dose	Consult with Sponsor regarding which visit days should be performed ( Table 9 – Table 23 ), perform dose step assessments as needed per Table 14a
	≥ 7 days	Run-in dose, dose step or target dose	Repeat the cycle and schedule of assessments ( Table 9 – Table 23 ) starting at day 1, perform dose step assessments as needed per Table 14

a If treatment is interrupted towards the end of cycle 1 after the target dose is reached, and the decision is made to not restart the infusion prior to day 29, only perform EOI assessments on Cycle 1 Day 29

In case of an infusion interruption of > 24 hours, regardless of the reason for interruption, restart of the infusion should be performed at the initial MTD (run in dose) and dose steps should be performed prior to administering the target dose. The dose level for each step and number of steps should be determined in consultation with the Sponsor prior to re-initiation of the infusion.

After two unsuccessful restarts, the subject will be considered as not DLT evaluable (if no DLT has been observed during treatment) and can be replaced. The subject may remain on the study and continue treatment with a previously tested target dose that has been well tolerated.

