Dexamethasone (8 mg IV) should be administered within 1 hour prior to restart and within 1 hour prior to the dose step(s). The subject should be hospitalized starting from restart of infusion until 72 hours after the dose step. After the dose step, assessments of vital signs, pulse oximetry and clinical evaluation should be performed as per the schedule of assessments for dose steps ([Table 14](#)).

The number of days of infusion at the target dose before and after an interruption should sum up to the planned duration, ie, minimum 10 days at the target dose for a 14 day

cycle, and minimum 14 days at the target dose for a 21 or 28 day cycle. In this case, the subject would still be DLT-evaluable. However, if the cycle was interrupted for more than 7 days, a new cycle should be started and the interrupted cycle would not be evaluable for DLT, unless the event that lead to the interruption was a DLT.

Please refer to the table below to determine the minimum duration of treatment for a subject to be counted as DLT evaluable.

**Note:** In case a treatment cycle is considered complete but lasted less than the planned number of days (14, 21, or 28, as applicable), the EOI bone marrow assessment should be performed once it was confirmed that the cycle will not be resumed in order to assess treatment response and determine the infusion-free interval prior to start of the next cycle, if applicable. Bone marrow and blood samples (for [REDACTED], immune cells, and plasma biomarker testing) should also be sent to the applicable central laboratories.

Planned Treatment Duration	Minimum Duration of Treatment at Target Dose to be Counted as DLT evaluable
2 weeks	7 days at target dose
3 weeks	14 days at target dose
4 weeks	14 days at target dose

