### Restart of Treatment after Infusion Interruption due to Cytokine Release Syndrome:

After interruption of AMG 330 infusion due to Grade 3 cytokine release syndrome, the infusion may be restarted if all of the following criteria are met:

- The Amgen medical monitor must be consulted prior to restarting treatment
- The event has resolved to grade  $\leq 1$  prior to restarting treatment

If the target dose is █ µg/day, AMG 330 therapy should be restarted at the MTD1 (█ µg/day) for 4 days before step up to an intermediate dose level of █ µg/day. If AMG 330 therapy at █ µg/day is well tolerated for 4 days (ie, absence of grade  $\geq 2$  CRS) then a dose step up to a target dose of █ µg/day can occur.

If the target dose is greater than █ µg/day, AMG 330 therapy should be restarted as described in Section 6.2.1.5. In case of an infusion interruption of  $> 24$  hours, regardless of the reason for interruption, restart of the infusion should be performed at the initial MTD (run in dose) and dose steps should be performed prior to administering the target dose. The dose level for each step and number of steps should be determined in consultation with the Sponsor prior to re-initiation of the infusion.

If a subject experiences 2 separate grade 3 CRS events, AMG 330 must be permanently discontinued.

Please also refer to the general guidance for restart of infusion after interruptions in Section 6.2.1.5.

For Grade 3 and 4 cytokine release syndrome, please see Section 6.2.1.4 for DLT considerations.

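### After a short interruption at target dose in a 3- or 4-week cycle, the target-dose days that make a subject DLT-evaluable can finish after the 4-week DLT window, and an event on those days is not counted by default

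*Protocol*

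**What the plan says.** **The DLT clock.** Protocol Section 6.2.1.4: "A DLT will be defined as any of the events described below occurring in a subject during the DLT window". The same section adds: "The DLT window will be 4 weeks, regardless of the length of the treatment cycle".

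**The evaluability clock.** Under DLT Evaluation in the same section, a subject is not evaluable who "has not received IP treatment for at least 14 days at the target dose for a 3- or 4-week cycle" (7 days for a 2-week cycle). Protocol Section 3.4 and SAP Section 6.2 repeat the rule. None of the three says that the days must fall within the window.

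**Restarts.** After an interruption of more than 24 hours, Section 6.2.1.5 says "restart of the infusion should be performed at the initial MTD (run in dose) and dose steps should be performed" before the target dose resumes. It then says: "The number of days of infusion at the target dose before and after an interruption should sum up to the planned duration", and concludes: "In this case, the subject would still be DLT-evaluable". Section 6.6 gives a restart schedule for one redacted target dose: the first-step dose "for 4 days before step up to an intermediate dose level", then 4 days at that level, which is 8 days before target.

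**Flexibility.** Section 6.2.1.4 allows the window to be extended where the DLT definition itself depends on time. It also lets the DLRT declare an out-of-window event a DLT. That vote must be unanimous, and the event must be judged possibly related and be more frequent, more severe or more persistent than expected. Section 10.3.2 and SAP Section 7.1 list the length of the DLT period among the matters on which the DLRT may make recommendations.

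**The concern.** Each subject's entry in the escalation table has two parts: whether the subject is in the denominator (target-dose days) and whether the subject is in the numerator (an event inside the window). If qualifying exposure can accrue after the window has closed, the two parts refer to different periods. A DLT-type event on a late qualifying day is then not a DLT by default. The subject enters as a non-DLT if the 14 days are completed, or is replaced as non-evaluable if they are not. In neither case does the event reach the numerator unless the DLRT acts.

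Cohorts are small, so one event matters. In Protocol Table 5, moving from 1/3 to 0/3 changes expansion to escalation, and moving from 2/6 to 1/6 changes de-escalation to escalation. In the SAP Section 3.3 mTPI-2 table for Groups 2 and 3, the same moves change stay to escalate and de-escalate to escalate.

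**Working it through.** **The plan's own figures.** Protocol Section 10.2 and SAP Section 3.2 give the chance of at least one DLT as 1 − (1 − p)^n:
- n = 3: 27.1% at p = 10%, 69.9% at p = 33% (stated 27-70%).
- n = 6: 46.9% and 91.0% (stated 47-91%).

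They reproduce. They assume that every DLT in an evaluable subject is counted.

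**Which restarts are involved.** Table 6 repeats the cycle from day 1 for any interruption over 24 hours in a 2-week cycle, for one of 24 hours to 7 days at run-in or step dose, and for any of 7 days or more. The case where days are simply summed is a 3- or 4-week cycle interrupted at target dose for more than 24 hours and less than 7 days, taken here as gaps of 2 to 6 whole days.

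**Timeline.** Let L1 be the lead-in days before first reaching target, g the gap, and L2 the lead-in days after restart. Assume the window is days 1-28 from first dose.
- 14th summed target-dose day = L1 + g + L2 + 14.
- It passes day 28 when L1 + g + L2 > 14.
- Qualifying days outside = the smaller of L1 + g + L2 − 14 and the target days still owed at restart.

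Most lead-in lengths are redacted. Section 3.1.1 allows 1 to 5 days for the run-in and for each step, so a range is shown:

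| L1 = L2 | 14th target day, g = 2 to 6 | Days outside (maximum) |
|---|---|---|
| 4 | 24 to 28 | 0 |
| 5 | 26 to 30 | 0 to 2 |
| 6 | 28 to 32 | 0 to 4 |
| 8 (Section 6.6) | 32 to 36 | 4 to 8 (29% to 57% of 14) |

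**Example.** Lead-in days 1-8, target days 9-14 (6 days), gap days 15-20 (6 days), lead-in days 21-28, target again from day 29. The remaining 14 − 6 = 8 qualifying days are days 29-36, all outside the window.

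**Possible effect on the 3+3 rule (illustration).** P(escalate) = (1 − p)^3 + 3p(1 − p)^5. Replace p by the counted rate p(1 − s·f), where s is the share of subjects restarted and f the share of qualifying days outside. The documents do not give s. The calculation also assumes a constant DLT risk over the qualifying days, that affected subjects stay in the denominator, and no DLRT vote. At a true rate of 33%:

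| s | f | Counted rate | P(at least 1), n = 3 | n = 6 | P(escalate) |
|---|---|---|---|---|---|
| any | 0 (clocks aligned) | 33.0% | 69.9% | 91.0% | 43.4% |
| 1/3 | 4/14 | 29.9% | 65.5% | 88.1% | 49.7% |
| 1/3 | 8/14 | 26.7% | 60.6% | 84.5% | 56.3% |
| 1 (upper bound) | 8/14 | 14.1% | 36.7% | 59.9% | 83.1% |

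**The case against.** The strongest reply is that the event would be seen. Adverse events are collected to end of study, and Section 10.3.1 puts those of all subjects before the dose level review. A restarted subject is not evaluable until the 14 days are complete, so if that subject is needed for the minimum of three, a day 29-36 event is already known when the cohort is judged. The DLRT can then vote. This stands as far as it goes: it is wrong to infer that the event necessarily goes uncounted, or that the window is rigid. It does not close the gap. The vote is discretionary, must be unanimous and carries extra conditions, and SAP Section 5.4 takes DLTs from the investigator's eCRF answer without describing a step for a DLRT decision.

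Second, most other restarts repeat the cycle, and the natural reading is that DLT assessment moves with it. No sentence says so.

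Third, the amendment history gives the purpose of the minimum-exposure rule as adequate exposure within the DLT window. On that reading the example subject would be non-evaluable. That is history, not operative text; the current rules do not include the restriction.

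Two stronger readings fail:
- A reader might infer that the 8 restart days make the minimum unreachable in shorter cycles (14 − 8 = 6 against 7; 21 − 8 = 13 against 14). Target days before the interruption also count, so one prior day gives 14 in the 21-day case. Also, 8 + 7 = 15 and 8 + 14 = 22 both fit within 28 days, Section 6.2.1.4 allows cycles to be extended, and nothing ties the 4 + 4 schedule to those cohorts.
- A reader might infer that interruptions come mainly from cytokine release, so that subjects with early toxicity are selectively credited. Section 6.2.1.5 lists six triggers, and the documents give no frequencies.

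**Conclusion.** The concern holds in a limited form. For 3- or 4-week cycles interrupted at target dose for more than 24 hours and less than 7 days, the rules as written allow qualifying exposure to finish after the window in which DLTs count. With 8-day lead-ins, up to 4-8 of the 14 days are affected; with lead-ins of 4 days or less, none. This rests on a window that starts at first dose, which the documents do not define, and on a lead-in given for only one redacted target dose. For repeated or new cycles the documents do not say whether the window restarts.

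This is a possible undercount, not a demonstrated downward bias. The share of subjects restarted is unknown. A share of days is not a share of risk: Section 6.6 places increased cytokine-release risk in the first few days after the initial infusion. The escalation probabilities above show only what the gap could do if nobody used the discretionary routes. The point still merits a change, because a single event decides between 2/6 and 1/6 and the remedy is cheap.

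**What to change.** In Protocol Sections 3.4 and 6.2.1.4 and SAP Section 6.2:
- State the day on which the DLT window starts.
- For a subject restarted within a cycle, run the window to the later of day 28 and the day the minimum target-dose exposure is complete.
- State that the window restarts with a repeated or new cycle.
- Hold the escalation decision until that subject's window closes.

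The cost is wording and a short wait for restarted subjects only: 4 to 8 days past day 28 in the 8-day lead-in case, and the window's own 4 weeks from the start of a repeated cycle.

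Two related conflicts need reconciling at the same time. For a 14-day cycle, the text of Section 6.2.1.5 gives a minimum of 10 target-dose days, while the table beneath it, Sections 3.4 and 6.2.1.4, and SAP Section 6.2 give 7. And Table 6 repeats the cycle for interruptions of 7 days or more, while the text of Section 6.2.1.5 starts a new cycle only after more than 7 days, so an interruption of exactly 7 days is treated in two ways.
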